9.7.3 Analysis of Safety Endpoint(s)/Outcome(s)

All objectives in this study are for the assessment of safety outcomes. Refer to Section 9.3.1 for the outcome definition and assessment.

9.8 Quality Control

The Investigator is to maintain a list of appropriately qualified persons to whom he/she has delegated study duties. All persons authorized to make entries and/or corrections on eCRFs will be included on the Amgen Delegation of Authority Form.

Source documents are original documents, data, and records from which the patient eCRF data are obtained. These include but are not limited to hospital records, clinical and office charts, laboratory and pharmacy records, diaries, microfiches, radiographs, and correspondence.

The Investigator and study staff are responsible for maintaining a comprehensive and centralized filing system of all study-related (essential) documentation, suitable for inspection at any time by representatives from Amgen and/or applicable regulatory authorities.

Documents to be maintained for the study are as follows:

- Patient files containing the completed CRF, informed consent forms, as applicable, and patient identification list
- Study files containing the protocol with all amendments, copies of pre-study documentation, and all correspondence to and from the Institutional Review Board (IRB)/Independent Ethics Committee (IEC) or other relevant ethical review board and Amgen

In addition, all original source documents supporting entries in the eCRFs must be maintained and be readily available. Retention of study documents will be governed by the contractual agreement with Amgen.

Amgen retains all data, programs and outputs generated for the study. At study close, data are uploaded from the Medidata Rave database and stored in accordance with Amgen Standard Operating Procedures (SOPs). Statistical programming and outputs are locked in the analysis environment and no updates are permitted; standard programming procedures will apply.

9.8.1 Study Monitoring and Data Collection

Source data verification will be performed at the study site, in accordance with Amgen SOPs. The Amgen representative(s) and regulatory authority inspectors are responsible for contacting and visiting the Investigator for the purpose of inspecting the facilities and, upon request, inspecting the various records of the clinical study (eg, eCRFs and other pertinent data) provided that patient confidentiality is respected.

The clinical monitor or designee is responsible for verifying the eCRFs at regular intervals throughout the study to verify adherence to the protocol completeness, accuracy, and consistency of the data; and adherence to local regulations on the conduct of research. The clinical monitor, or designee is to have access to patient medical records and other study-related records needed to verify the entries on the eCRFs in accordance with the local laws and regulations.

The Investigator agrees to cooperate with the Clinical Monitor, or designee to ensure that any problems detected in the course of these monitoring visits, including delays in completing eCRFs, are resolved.

In accordance with the sponsor's audit plans, this study may be selected for audit by representatives from Amgen's Global Compliance Auditing function (or designees). Review of study-related records will occur to evaluate the study conduct and compliance with the protocol, and applicable regulatory requirements.

Data capture for this study is planned to be electronic:

- All source documentation supporting entries into the eCRFs must be maintained and readily available.
- Updates to eCRFs will be automatically documented through the software's "audit trail".
- To ensure the quality of clinical data across all patient and sites, a clinical data management review is performed on patient data received at Amgen. During this review, patient data is checked for consistency, omissions, and any apparent discrepancies. To resolve any questions arising from the clinical data management review process, data queries and/or site notifications are created in the EDC system database for site resolution and closed by Amgen reviewer.

The Investigator signs only the Investigator Verification Form for this electronic data capture study. This signature indicates that the Investigator inspected or reviewed the data on the eCRF, the data queries, and site notifications, and agrees with the content.

9.8.2 Investigator Responsibilities for Data Collection

The Investigator is responsible to comply with the protocol requirements for all assessments and data as stipulated in the protocol for each patient in the study.

9.8.3 Validity and Reliability

The data collected for this study will be abstracted from patient records that are kept for the documentation and decision-making regarding patient care. Abstractors will be trained on the eCRF, prior to the start of data collection for the study. Automatic edit checks within the database and further manual review by the sponsor help to ensure quality and completeness of the data. Data queries are sent to site for clarification and resolution of discrepancies.

9.9 Limitations of the Research Methods

There is a risk of measurement error when data that were entered in the past were unclear or incomplete. Missing information may also occur in patients receiving care throughout their treatment history at more than one site and, therefore, the participating site may not have all the details requested. Additionally, during treatment outpatient visits may occur at a different site so this information may be underreported for those patients. This would lead to bias if the information was not missing at random.

It is possible that not all eligible patients could be included due to not consenting to be in the study potentially leading to bias if the excluded patients are systematically different from the included patients.

Information bias is another possible bias if, for example, the information for more complicated patients was recorded with more or less detail. Additionally, there may be missing information on outcomes.

Confounding may be possible in the comparison analysis. To account for any potential confounding of outcomes, baseline characteristics of the two treatment groups (blinatumomab versus chemotherapy) will be evaluated for differences and then input as a covariate in regression models if differences are observed.

The sites to be included in this study are expected to be larger treatment centers that specialize in treatment of patients with ALL due to the size of the patient population even though an effort will be made to include smaller treatment centers for representative purposes. Therefore, there might be a bias towards larger centers where a difference in medical practice or patient mix compared with smaller treatment centers could exist and this could affect generalizability of the study findings. It is possible that different sites or countries may use slightly different criteria to assess certain study endpoints (eg, response to treatment), potentially resulting in systematic differences. To examine this, endpoints will be tabulated by country to assess any systematic differences.

10. Protection of Human Subjects

This study will comply with all relevant ethical and regulatory requirements in each country and will not be used for the conduct of marketing surveys or other marketing purposes. The study will comply with Amgen AE reporting standard operating procedures. This study and data collection will be conducted in accordance with the relevant local laws.

The Responsible Physician is also responsible for forwarding the following documents to Amgen or its representative for review before study initiation occurs:

- Signed and dated protocol signature page (Responsible Physician 's Agreement)
- Copy of the Central Ethics Board approval of the protocol, waiver for requirement of informed consent
- Patient or patient's legally acceptable representative has provided informed consent (for countries where required per local regulations)
- Up-to-date curriculum vitae of Responsible Physician and all co/sub-physicians
- Signed confidentiality agreement
- Signed study contract

The Responsible Physician will be charged with maintaining correct and comprehensive documentation, while the Amgen monitor/designee is tasked to ensure that the Responsible Physician is following the correct study protocol.

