9.2.2 Selection and Number of Sites

Sites participating in Study 20120215 may be selected (planned in Europe, Israel, Australia, and Latin America) and further centers located in (but not limited to) Europe, Israel, Australia, Brazil, Canada, Mexico, United States, outside of Study 20120215 are planned to be included in this 20180130 study. The final number (and locations) of sites has not been confirmed.

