9.2.3 Patient Eligibility

9.2.3.1 Inclusion Criteria

Patients are eligible to be included in the study if they meet all of the following inclusion criteria.

- Paediatric B-cell precursor ALL patients with any indication world-wide that received blinatumomab or chemotherapy in routine clinical practice, followed by transplantation, or EU paediatric indications that may be authorized in the future. This means that paediatric patients which receive blinatumomab off-label in the EU or with a different indication in ex-EU regions may be included in the study.
- Patient's legally acceptable representative has provided informed consent when the patient is legally too young to provide informed consent and the patient has provided written assent based on local regulations and/or guidelines prior to any study-specific activities/procedures being initiated.

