Regulation (inhibit, self-monitor), Emotion Regulation (shift, emotional control), and Cognitive Regulation (initiate, working memory, plan/organize, task monitor, organization of materials). For patients ages 19+, the informant report form will be completed by a parent (guardian) or other adult who knows the patient well (BRIEF-A Informant); skills are evaluated in the areas of Behavioral Regulation (inhibit, shift, emotional control, self-monitor) and Metacognition (initiate, working memory, plan/organize, task monitor, organization of materials). The BRIEF will be re-administered to patients ages 2-5 years every 6 months in order to capture the more rapid rate of typical development; parents (guardian) or informants of patients ages 6 years and older will complete the form every year.

- A complete written manual describing administration and scoring procedures will be created by study neuropsychologist who has thorough knowledge of and experience with these measures. Initial personalized training of these procedures with study personnel will also be provided, along with ongoing consultation as needed.
- Neurological impairment defined as:
 - Peripheral nervous system disorders (including neuromuscular junction)
 - Central nervous system disorders
- Endocrine impairment defined as:
 - Hypothalamus-Pituitary-Gonadal Axis disorders
 - Hypothalamus-Pituitary-Adrenal (HPA) Axis disorders
 - Hypothalamus-Pituitary-GH Axis disorders
 - Hypothalamus-Pituitary-Thyroid Axis disorders
- o Immune system impairment defined as:
 - leukopenia (neutropenia and/or lymphopenia)
 - Iow IgG
 - low IgM
 - low IgA
 - Autoimmune disorders
 - Vaccination failure

Secondary Objectives

- HSCT-related AE defined as any second malignancy; Graft versus Host Disease (GvHD); infection, and/or; relapse
 - o Acute GvHD data includes
 - Grading of disease by either National Institute of Health (NIH) or Seattle Criteria
 - Organ involvement: skin; gut; liver; lung; eye; mouth' musculoskeletal, and/or; other

- GvHD associated symptoms: thrombocytopenia (<100 G/l); eosinophilia (Absolute Eosin Count: AEC > 500x10/L); bronchiolitis obliterans; bronchiolitis obliterans organizing pneumonia (BOOP); polyserositis, and; other
- Resolution
- Chronic GvHD data includes:
 - Diagnosis based upon clinical or histological evidence
 - Diagnosis of progressive, quiescent, or de novo disease
 - Grading of disease by either NIH or Seattle Criteria

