9.3.2 Covariate Assessment

Baseline

- Recording of ALL-related diagnoses history both prior to and following blinatumomab/SOC chemotherapy
 - Disease status (prior to blinatumomab/SOC chemotherapy)
 - MRD status (following treatment; MRD positivity defined at a level $\ge 10^{-4}$ in PCR and/or flow quantification)
 - Relapse (following treatment)
 - Time point of relapse (time since primary diagnosis and time after completion of primary therapy)
 - Whether extramedullary relapse
 - Bone marrow status at relapse
 - Secondary malignancy (following treatment)
- Recording of ALL-related treatment history
 - Details of SOC-chemotherapy therapy
 - Specific therapy
 - Duration of therapy
 - Details of blinatumomab therapy
 - Number of blinatumomab cycles
 - Occurrence of further blinatumomab therapy following initial discontinuation
 - Duration of blinatumomab therapy
- Recording of alloHSCT status
 - Occurrence of alloHSCT
 - Interval between SOC-chemotherapy/blinatumomab and alloHSCT
- Clinically relevant events prior to initiation of therapy or after initiation of therapy and before alloHSCT (see definitions above)
 - Neurological event
 - Endocrine event (including evidence of growth delay)
 - o Immune event
 - Toxicity (gastrointestinal, hematologic, dermatology, cardiac, pulmonary, hepatic, renal, infection, skeletal, etc.: see definitions above)
- Other important clinical factors
 - o Comorbidity
 - Concomitant medication
 - Prenatal development
 - High-risk pregnancy
 - Delivery complications including hypoxia
 - o Gestational time at the delivery
 - APGAR score
 - o Gestational weight (intrauterine growth restriction [IUGR])
 - Psychomotor development impairment and psychiatric conditions recognised prior to the therapy
- Pregnancy and breastfeeding status after blinatumomab initiation

Follow-up

- Demographics and clinical characteristics including comorbidity
 - All treatments for ALL
 - Pregnancy and breastfeeding status

- Recording of further ALL-related treatment history
 - Details of SOC-chemotherapy therapy: specific therapy, and; duration of therapy
 - Details of blinatumomab therapy: number of cycles; occurrence of further blinatumomab therapy following initial discontinuation, and; duration of therapy
- Further HSCT
 - Occurrence of HSCT
 - o Interval between SOC-chemotherapy/blinatumomab and HSCT
 - Outcome of HSCT: early/late GvHD; infection; HSCT-related toxicity (see definitions above)

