9.7.2.2.3 Analysis of the Primary and Secondary Endpoints

Patient incidence proportions (and 95% Cls) for each of the specified outcome events will be summarized. KM estimates for time to first onset of each specified event will be provided.

For the events of interest, events that occur after a relapse or secondary malignancy will be censored as it is unlikely that events that occur after relapsed and treatment for relapse could be considered related to initial chemotherapy or blinatumomab treatment for the prior disease occurrence.

A comparison between the blinatumomab versus chemotherapy group will be conducted at the final follow-up in the study pending adequate sample size is enrolled $(\geq 50 \text{ patients per arm})$ and the blinatumomab and SOC groups are comparable (eg. there is overlap between PS distributions across the two groups, or no critical differences that cannot be accounted/adjusted for). Prior to comparison being conducted, covariates listed in Section 9.3.2 will be evaluated for differences between the two groups. Any covariates that are not comparable between the two (Wald chi-square or t-test, p-value < 0.25), will be evaluated as a covariate for adjustment in the models. The primary and secondary endpoint of discrete events (eg, incidence endpoints) will be compared by a logistic regression which will generate an odds ratio and 95% confidence interval of the odds of developing an event. Endpoints that are time-to-event will be compared by a Cox regression model which will generate hazard ratio and 95% confidence interval for the risk of developing an event. Also, we will additionally conduct a propensity score weighting analysis based on the covariates collected for this study. An additional sensitivity analysis may be done to adjust for the drop-in effect of patients receiving anti-cancer medications during follow-up.

A literature review of published data at the time of the final study report will be performed for the relevant endpoints. If there is any relevant scientific data publicly available by the time when the study ends (> 12 years later), Amgen will provide a comparative analysis. If a sufficient number of patients are identified in publicly available database with information on relevant confounding factors, Amgen will conduct a direct comparative analysis, but descriptive analyses will be undertaken either way.

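### Section 9.9 meets possible country differences in endpoint assessment with a table only; nothing requires region in the blinatumomab–chemotherapy comparison

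*Protocol*

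**What the plan says.** Protocol Section 9.9 lists as a limitation that "different sites or countries may use slightly different criteria to assess certain study endpoints" and adds that systematic differences could result. The stated response is "To examine this, endpoints will be tabulated by country to assess any systematic differences".

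Section 9.2.3.1 says that "paediatric patients which receive blinatumomab off-label in the EU or with a different indication in ex-EU regions may be included in the study". Section 9.2.2 plans sites taking part in Study 20120215 and "further centers located in (but not limited to) Europe, Israel, Australia, Brazil, Canada, Mexico, United States".

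For the arm comparison, Section 9.7.2.2.3 says that "covariates listed in Section 9.3.2 will be evaluated for differences between the two groups". Those that differ at p < 0.25 are considered for the logistic and Cox models. A propensity score weighting analysis is added, using the covariates collected for the study. The comparison goes ahead only if there are at least 50 patients per arm and the groups are comparable, for example because the propensity scores overlap.

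Section 9.3.2 does not list country, region or site. Its nearest entry, "Demographics and clinical characteristics including comorbidity", stands under follow-up rather than baseline. Country and site do appear in Section 9.7.2.2.1, where patient numbers are tabulated by each.

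**The concern.** A factor biases a treatment comparison when it is related both to which treatment patients received and to how often the outcome is recorded. The protocol concedes the second link in general terms. Apart from the neuropsychomotor questionnaires, outcomes are abstracted from routine charts. In Section 9.3.1, low immunoglobulins and endocrine axis disorders carry no cut-off or testing schedule, so recorded incidence can depend on how often a centre tests and what it counts.

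The protocol makes the first link plausible. Section 7.1.3 describes a 2014 FDA approval covering children and a 2015 EMA approval for adults. Section 9.7.2.2.4 contrasts a narrower EU paediatric indication with the indications outside it.

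At stake is the interpretation of the odds and hazard ratios in a study that Section 7.2 describes as a category 1 commitment to the EMA. If one arm comes more from centres that test often, the ratio partly measures where patients were treated.

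**Working it through.** **1. Scale of the planned comparison (Section 9.5).** For 98% versus 88% with 52 survivors per arm, the pooled proportion is 0.93 and SE = √(2 × 0.93 × 0.07 / 52) = 0.0500. Then z = 0.10 / 0.0500 = 2.00 and two-sided p = 0.0457; the protocol gives 0.0455. Also 52 / 0.35 = 148.6, so 149 per arm and 298 in total, as stated. Section 9.5 treats the 10-point difference as clinically significant.

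**2. What each route does with country.**

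| Route | Source of variables | Country, region or site |
|---|---|---|
| Logistic and Cox models (9.7.2.2.3) | Section 9.3.2, p < 0.25 screen | Not named |
| Propensity score weighting (9.7.2.2.3) | Covariates collected for the study | Allowed, not required |
| Comparability condition (9.7.2.2.3) | Overlap of propensity scores, or no critical differences that cannot be adjusted for | Only if the score or that judgement includes it |
| Endpoint table (9.9) | Country | Shown, not adjusted for; not stated to be within arm |

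**3. Size if the arms draw differently on two regions.** Take no drug effect, recorded incidences rA and rB in regions A and B, and a share of patients from region A of s1 in one arm and s0 in the other. Then

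spurious difference = (s1 − s0) × (rA − rB).

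The documents give neither shares nor regional incidences, so every input here is an assumption.

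- 75/25 versus 25/75, 10-point gap: 0.50 × 10 = 5 points.
- Same mix, 13-point gap (the full 85%–98% span in Section 9.5): 0.50 × 13 = 6.5 points.
- 60/40 versus 40/60, 10-point gap: 0.20 × 10 = 2 points.
- 90/10 versus 10/90, 10-point gap: 0.80 × 10 = 8 points.
- Equal mix in both arms: 0 points, whatever the gap.

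With assumed regional incidences of 98% and 88%, an unadjusted pooled z-test at nominal 5% would reject as follows:

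| Regional mix | Spurious difference | Odds ratio | 52 per arm | 149 per arm |
|---|---|---|---|---|
| 50/50 v 50/50 | 0 | 1.00 | 5.0% | 5.0% |
| 60/40 v 40/60 | 2 points | 1.36 | 6.8% | 10.4% |
| 70/30 v 30/70 | 4 points | 1.88 | 12.5% | 27.2% |
| 80/20 v 20/80 | 6 points | 2.67 | 22.3% | 52.8% |
| 90/10 v 10/90 | 8 points | 4.00 | 35.7% | 77.5% |

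Comparing within region gives zero spurious difference in every row, because the arms have equal incidence inside each region.

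**4. How much regional adjustment the data can carry.** At the Section 9.5 figures, non-events among 104 survivors number 52 × 0.02 + 52 × 0.12 = 1.04 + 6.24, or about 7. A logistic model for that outcome with several region terms could fail through separation, which limits what the fix can ask for.

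**The case against.** The strongest reply is that the protocol does not shut country out. The list in Section 9.3.2 governs only the regression screen, and the propensity score draws on all collected covariates. Section 4 puts demographics first among the covariates without a follow-up restriction, and Section 9.9 promises to examine baseline characteristics for differences. This stands. A reader might infer that the propensity score omits country, but the text does not say so; it leaves the choice open.

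Second, the comparison is conditional on comparable groups. That is a real safeguard, but an overlap check detects regional separation only if region is in the score.

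Third, a reader might infer that the protocol shows treatment to depend on region, so that country is an established confounder. It does not. Section 9.2.3.1 says who may be enrolled and is silent on the arm ratio by country.

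Fourth, the only example Section 9.9 gives of differing criteria is response to treatment, which is not a listed endpoint, and the text speaks of slight differences. Several endpoints are standardised: the questionnaires have score thresholds and training, relapse has common criteria in Appendix F, and survival is death. The entry "Grading of disease by either National Institute of Health (NIH) or Seattle Criteria" concerns the grade of GvHD, whereas the endpoint is its occurrence. This narrows the concern mainly to the immune, endocrine, neurological and adverse-event outcomes taken from charts. It does not remove it, since the sentence in Section 9.9 covers study endpoints generally.

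Finally, model details may sit in a statistical analysis plan that is not shown. But the protocol itself fixes the regression pool by pointing to Section 9.3.2, and itself names a tabulation as the answer to country differences.

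**Conclusion.** The point holds as a gap between an acknowledged problem and its remedy. Followed as written, the plan could reach its final odds and hazard ratios without region in any model, and the country table would not correct them.

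Bias arises only if recorded incidence differs by region for reasons of practice and the arms also differ in regional mix. The first is conceded as possible and the second is plausible but not stated. The size is therefore unknown: 5 points under the 75/25 and 10-point assumptions, and nothing if the mix is equal. Reaching the 10-point benchmark at a 75/25 mix would need a 20-point regional gap, wider than the 13-point span that Section 9.5 expects for having at least one event. The documents do not support saying that the comparison is confounded, only that it is not protected against this. It should be settled before the final analysis, so that region is not a choice made after outcomes are seen.

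**What to change.** - In Section 9.3.2, add region to the baseline covariates, with countries in a few broad groups fixed in advance.
- In Section 9.7.2.2.3, always include region in the propensity score and in the overlap check, whatever the p < 0.25 screen shows.
- Adjust or stratify the logistic and Cox models by region where event and non-event counts allow; otherwise rely on the weighted analysis, and say so.
- In Section 9.9, tabulate endpoints by country within treatment arm.

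No new data should be needed, since Section 9.7.2.2.1 already tabulates patients by country and site. The cost is wording, a somewhat wider confidence interval and the pooling of small countries. Forcing region into every logistic model is not advised, given about 7 expected non-events at the design figures.
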